In Session 1 (pre-medication baseline), we will collect baseline measures of smoking urge, withdrawal symptoms, mood, cognitive performance, a behavioral economics-based measure of cigarette demand and effects of smoking a cigarette on cigarette reward, satisfaction and mood. Next, participants will be randomized to VAR (1 mg twice daily for 3 weeks) or PLA, using urn randomization to stratify on gender and dependence. Participants will complete a week of medication use using the standard dose run-up (0.5 mg once daily on days 1-3, 0.5 mg twice daily on days 4-7, then 1 mg twice daily until the end of the medication period). In Session 2, which occurs after one week on medication, participants will complete the same laboratory assessments as in Session 1. Next, participants will undergo a 3-day abstinence period. They will come to the laboratory twice per day and will receive escalating cash incentives for breath carbon monoxide (CO)-verified abstinence. At each visit, cigarette craving and withdrawal symptoms will be measured. At Session 8 (Thursday morning), participants who have been continuously abstinent will complete the same procedure as in Sessions 1. For ethical reasons, participants who complete the study through Thursday and who wish to remain abstinent may opt out of smoking during this session and will still receive full compensation for participation, as long as they attend this lab session and complete the other session measures.

Participants will be asked to return to the laboratory on Friday morning. Breath CO will be measured and time of first lapse (single cigarette) and relapse (return to regular smoking) will be collected among those who have lapsed and relapsed. Those still abstinent ($CO \leq 4$ ppm) since Session 8 will receive a small cash incentive. Next, participants will be shown how to use breath CO monitors with smart phones to record

and text us videos of themselves providing CO samples twice per day for the following week to determine time to lapse and relapse. Participants will receive \$5 for each submitted sample (not contingent on CO level), paid when the smart phone and CO monitor are returned at the end of the week.

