All data will be collected for research purposes only. All forms will be marked with only subject ID, session number and date. All records will be stored in locked files (physical or on computer) in locked rooms accessible only to research staff. Data gathered from people who attend the screening but do not meet inclusion criteria or decide not to participate will be stripped of personal identifiers or links and only the reason for study exclusion will be kept.

Personal information (participant name, address, telephone number, email address, locator contact information) must be collected so that the research assistant can contact people to schedule assessments, call with session reminders and arrange transportation to sessions. These data will be stored in a locked file that does not contain ID code numbers. All other data will be stored in files locked in a separate location with only code numbers identifying subjects and no personal identifiers. A cross-index of code numbers and participant names will be kept in a separate, password-protected computer file that is available only to research staff, PI, and mandated agencies during audits (e.g., study sponsor and Brown University IRB).

Saliva specimens for cotinine analysis will be marked with a study ID number, stored in the locked laboratory suite, and sent to a commercial laboratory for analysis. We will track samples sent and analysis results received using a form stored on a password-protected computer.

Data Analysis Plan

R21 phase

Variables will be examined for distributional assumptions associated with analyses to be used and transformed if necessary. Groups will be compared on demographic and other individual difference measures using t-tests for continuous measures and chi-square tests for categorical measures. Analyses of the effects of Group (VAR, PLA) and Time (Sessions 2-8) on QSU and MNWS-negative affect scores will be conducted using generalized estimating equation (GEE) models (Zeger et al., 1988), which allow for varying numbers of observations per participant (to minimize bias due to attrition) while controlling for autocorrelation (AR1 structure). GEE will also be used to analyze the effects of Group and Time (Screening, Sessions 2 and 8) on BPRS and other psychiatric symptom scores. Mixed 2 x 2 Analysis of Variance tests (ANOVAs) will be used to examine effects of Group and Abstinence (Sessions 1 and 8) on CEQ scale scores,

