cognitive measure scores (with baseline scores covaried), CPT demand indices and within-session changes (post- minus pre-smoking) in CO level and positive and negative mood scale scores. Significant interactions will be followed by simple effects tests. Those who opt not to smoke in Session 8 will not be included in the Group x Abstinence analyses of CEQ, or pre-to-post smoking changes in CO or mood, but will be included in all other analyses (only one SS opted not to smoke in Session 8 in our previous study, Tidey et al., 2014). Latency to relapse will be defined as hours between the start of Session 8 and time of relapse, collected in person at Friday's session and by videoed CO sample in the follow-up week. We will follow up for one week after Friday's session, which is 8 days after Session 8. Thus, the maximum latency until second lapse will be 192 h, at which point data will be censored. Lapse latencies will be compared in VAR vs. PLA using a t-test. We will examine whether gender and FTND score (≤ 5 vs. ≥ 6) moderate the effects of VAR by adding these factors (separately) to each model.

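### In the R21 ANOVAs, the Abstinence factor (Session 1 v Session 8) mixes starting varenicline with abstaining; Session 2, which could separate them, is not used there

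*Combined protocol and SAP*

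**What the plan says.** The Brief Description of Protocol sets out three states for the R21 laboratory sessions.

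- Session 1, no drug and smoking: "In Session 1 (pre-medication baseline), we will collect baseline measures of smoking urge" and the other measures. Randomisation follows.
- Session 2, on varenicline or placebo and not yet abstinent: "In Session 2, which occurs after one week on medication, participants will complete the same laboratory assessments as in Session 1".
- Abstinence begins only after that: "Next, participants will undergo a 3-day abstinence period".
- Session 8, on varenicline or placebo and abstinent: "At Session 8 (Thursday morning), participants who have been continuously abstinent will complete the same procedure as in Sessions 1".

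The Data Analysis Plan, R21 phase, then states "Mixed 2 x 2 Analysis of Variance tests (ANOVAs) will be used" for "effects of Group and Abstinence (Sessions 1 and 8) on CEQ scale scores". The same models cover "cognitive measure scores (with baseline scores covaried), CPT demand indices and within-session changes (post- minus pre-smoking) in CO level", and the corresponding mood changes. A significant interaction leads to simple-effects tests, but the plan does not say which factor is tested within levels of which.

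The same section does use Session 2 elsewhere: in the GEE models for smoking urge and negative affect (Sessions 2 to 8) and for psychiatric symptoms (screening, Sessions 2 and 8). It gives no reason for leaving it out of the ANOVAs.

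**The concern.** A factor called Abstinence should compare sessions that differ in abstinence. In the placebo arm, Sessions 1 and 8 do, apart from time, practice and placebo response. In the varenicline arm they also differ in whether the participant is taking the drug. Any drug effect already present while smoking freely therefore enters the Abstinence main effect and the Abstinence comparison within varenicline.

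The CEQ satisfaction, reward and craving-reduction scales are listed among the primary outcome variables, as secondary targets. The sample-size section claims power for main as well as interaction effects on these targets, so the Abstinence main effect is among the tests the plan relies on. At stake is a wrong statement about what abstinence does to reinforcement, cognition or demand, in either direction: a spurious effect, or a real one cancelled by an opposing drug effect.

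**Working it through.** **The plan's own figure.** No stated number rests on this factor, but the 80% power claim sets the scale. Inputs from Power Calculation and Sample Size: N = 48, d = .40, so f = 0.20. The correlation rho is called moderate, without a value. For two sessions the noncentrality of the within-subject and interaction terms is f² x N x 2/(1 - rho).

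- rho = 0.5: 0.04 x 48 x 2/0.5 = 7.68, power 0.774.
- rho = 0.53: 0.04 x 48 x 2/0.47 = 8.17, power 0.799.

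So 80% is reachable for these terms near rho = 0.53. For the interaction, f = 0.20 corresponds to a between-arm difference in change of 0.80 SD.

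**Expected cell means.** Let D be the drug effect present before abstinence, A the abstinence effect without drug, X the extra effect of drug and abstinence together, and T2 and T8 the time, practice and placebo effects common to both arms.

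| Session | Placebo | Varenicline |
|---|---|---|
| 1 | m | m |
| 2 | m + T2 | m + T2 + D |
| 8 | m + T8 + A | m + T8 + D + A + X |

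| Term | Session 1 v 8 (planned) | Session 2 v 8 |
|---|---|---|
| Change, placebo | A + T8 | A + T8 - T2 |
| Change, varenicline | A + T8 + D + X | A + X + T8 - T2 |
| Main effect | A + X/2 + T8 + D/2 | A + X/2 + T8 - T2 |
| Group x factor | D + X | X |

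Apart from common time effects, the planned main effect is off by D/2 and the simple effect within varenicline by D. The placebo arm carries no drug term. The planned interaction is the total drug effect, D + X; it cannot separate D from X. None of this depends on rho.

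**Size.** Assumptions: 24 per arm, SD 1, equal correlation between sessions, no time effects, everyone contributing to Session 8, two-sided 0.05. Take D = -0.40, A = X = 0, rho = 0.5. The variance of a change score is 2(1 - 0.5) = 1.

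- Main effect: expected -0.20, SE = 1/sqrt(48) = 0.144, ratio 1.39.
- Simple effect within varenicline: expected -0.40, SE = 1/sqrt(24) = 0.204, ratio 1.96.

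Simulation with 20,000 trials per setting gave these rejection rates.

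| D | rho | Main effect, 1 v 8 | Within varenicline, 1 v 8 | Within placebo, 1 v 8 | Main effect, 2 v 8 |
|---|---|---|---|---|---|
| -0.40 | 0.3 | 21% | 37% | 5% | 5% |
| -0.40 | 0.5 | 28% | 49% | 5% | 5% |
| -0.40 | 0.7 | 41% | 69% | 5% | 5% |
| -0.80 | 0.3 | 63% | 90% | 5% | 5% |
| -0.80 | 0.5 | 77% | 97% | 5% | 5% |
| -0.80 | 0.7 | 94% | nearly 100% | 5% | 5% |

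**Masking.** With A = +0.40, D = -0.80, X = 0 and rho = 0.5, the planned main effect is 0.40 - 0.80/2 = 0.00 and is rejected 5% of the time. Session 2 v 8 recovers +0.40 and is rejected 78% of the time.

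**What the added contrast can do.** For a between-arm difference in change of 0.40 SD, the noncentrality is 0.40²/[2(1 - rho) x 4/48]. Power is 0.21 at rho = 0.3, 0.27 at 0.5 and 0.42 at 0.7. The Group x (2 v 8) test will often be inconclusive.

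**The case against.** The strongest defence is that the planned contrast answers the stated aim. Aim 1 asks for the effect of varenicline versus placebo on the reinforcing effects of a lapse, and the summary of analyses places satisfaction and reward at Session 8. That calls for the total drug effect at Session 8, and Session 1 is the only laboratory session before randomisation. If varenicline lowers satisfaction equally at Sessions 2 and 8, the lapse target has still been lowered. No aim asks for a drug effect over and above one present while smoking. This stands, and it is why the Group x (1 v 8) comparison should be kept.

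A reader might infer more: that the whole drug effect will be reported as an abstinence effect, that Aim 1 cannot be answered, or that Session 2 is discarded. The documents support none of these. The interaction is a difference in change between arms, not an effect of abstinence. The simple effects are unspecified, and testing Group at Session 8 would be a pure drug comparison. Only half of D enters the main effect. Session 2 is missing from these ANOVAs only; the two primary targets are modelled with it.

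The defence is also right that Session 2 v 8 is not clean. Session 2 falls at the end of the dose run-up and Session 8 later in the schedule, so if the drug effect differs by g between them, that contrast carries g/2 in its main effect and g in its interaction. The extra contrasts also multiply over many outcomes tested at an unadjusted .05.

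It does not rescue the Abstinence main effect or the Abstinence comparison within varenicline. Nothing in the documents separates drug from abstinence in those two terms.

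**Conclusion.** The point holds for the pooled Abstinence main effect (bias D/2) and the simple Abstinence effect within varenicline (bias D). These biases follow from the session schedule by algebra. The error rates are illustrations: 21% to 41% false rejection of the main effect for D = -0.40 SD over rho 0.3 to 0.7. They rest on assumed values of D and rho, equal arms, and complete Session 8 data.

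The Group x (1 v 8) interaction remains a usable total effect for Aim 1, with the limit that Session 8 is confined to continuously abstinent participants and so is not a fully randomised comparison. What it cannot show is whether the drug effect is specific to abstinence. The go/no-go rule is not expressed through the Abstinence factor, and this point does not reach it. This is a correction of interpretation that is worth making, not a defect that disables the trial.

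**What to change.** In the Data Analysis Plan, R21 phase:

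1. Rename the factor Session and give it levels 1, 2 and 8 for the outcomes in these ANOVAs.
2. Keep the Session 1-adjusted Group difference at Session 8 as the main drug-effect estimate.
3. Add two planned secondary contrasts: Session 1 v 2 (medication while smoking) and Session 2 v 8 (abstinence while on medication). Base any conclusion about abstinence on Session 2 v 8 and on the placebo arm.
4. State which simple effects will be tested.
5. State the limits: Session 2 is at the end of the run-up and Session 8 later in the dosing schedule; Session 8 includes only continuously abstinent participants, and those who opt out of smoking are excluded from the smoking-dependent measures; and Group x (2 v 8) has low power at N = 48.

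No new visit or procedure is needed, because Session 2 already repeats the Session 1 assessments. The cost is SAP wording and two further contrasts for each CEQ scale, cognitive measure, purchase-task index and within-session change. They should be labelled secondary, so that they are not read as additional confirmatory tests.

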A total of 48 randomized participants are planned for the R21 phase. This sample size is based on Aim 1, which is to determine effects of VAR versus PLA on smoking urges and negative affect during abstinence, reinforcing effects of a smoking lapse, cognitive function and time to relapse in SS. A repeated-measures design with 48 total participants provides 80% power to detect main and interaction effects on the primary targets (smoking urges and negative affect during abstinence) and secondary targets (reinforcing effects of a smoking lapse) of at least $d = .40$ in size, assuming a moderate within-subject autocorrelation. While this effect size is somewhat smaller than those detected by West et al. (2008) for effects of abstinence on urges and negative affect during abstinence and smoking satisfaction and reward from relapse (d 's = .32-.44), abstinence was not controlled or biochemically verified after target quit date in that study, and, as the authors noted, it is possible that the effects that they observed were due only to those who were completely abstinent. With our rigorous control of abstinence, which includes twice-daily CO testing and a stringent abstinence criterion, we believe that we will detect smaller effects. We are not determining sample size based on Aim 2 (which is to examine the extent to which the effects of VAR on time to relapse are mediated through its effects on the target mechanisms), but we should be able to

detect medium-sized group effects on latency to second lapse, and estimate the size of mediation relationships that would be detectable as significant. We anticipate 20% attrition between enrollment and randomization. Therefore, we anticipate needing to enroll up to 60 participants (30 per group) to include 48 in the intent-to-treat sample.

R33 phase:

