Mediation of the relationship between group and lapse latency will be examined using an SPSS macro (Preacher & Hayes, 2004). Hypothesized mediators will include baseline Calgary scale, cognitive performance and Contemplation Ladder scores, Session 8 QSU and MNWS scores, Session 8 CPT and CEQ Reward and Satisfaction scores, and Session 8 cognitive performance scores. Simple mediator models will be used to investigate the direct effect of medication on relapse latency (c path) with no mediator in the equation, as well as the medication \rightarrow mediator path (a), the mediator \rightarrow latency path (b), and the effect of medication on latency with the mediator in the equation (c' path). The indirect effect of medication on latency via each mediator ($c - c'$) is equal to the product of the coefficients of the "a" and "b" paths (i.e., "ab"). If ab is not normally distributed, 10,000 bootstrap resamples will be used to obtain lower and upper 95% confidence intervals (CI) for each indirect effect (Preacher & Hayes, 2008). All variables will be standardized first so that path coefficients can be directly compared across variables with different metrics. In addition, step-wise regression will be used to examine whether screening BPRS scores (entered in Step 1) and Session 8 BPRS scores (Step 2) predict latency to relapse. The SPSS mainframe statistical package (SPSS, Inc., Chicago, IL) will be used for GEE, mediation and regression analyses. All other analyses will be conducted using SPSS Statistics Version 20 for Windows (IBM, Armonk, NY). Differences will be considered significant when $p \leq .05$.

R33 phase

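### In the R21 cognitive ANOVA, Session 1 is both a level of Abstinence and the covariate, so the Abstinence main effect is miscalibrated; the VAR versus PLA comparison is not affected

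*Combined protocol and SAP*

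**What the plan says.** The Data Analysis Plan (R21 phase) specifies mixed 2 x 2 ANOVAs for "effects of Group and Abstinence (Sessions 1 and 8". The list of outcomes for these models includes "cognitive measure scores (with baseline scores covaried". Significant interactions are to be followed by simple effects tests, which are not specified further.

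The sentence does not say which session is the baseline. The R21 session description in the Summary of the Protocol does: "In Session 1 (pre-medication baseline), we will collect baseline measures of smoking urge, withdrawal symptoms, mood, cognitive performance". It also says that at Session 8 "participants who have been continuously abstinent will complete the same procedure as in Sessions 1". The mediation paragraph likewise lists baseline cognition apart from Session 8 cognition: "Hypothesized mediators will include baseline Calgary scale, cognitive performance and Contemplation Ladder scores". Where the plan uses a different reference visit, it names it, as it does with Screening for the psychiatric scales. No R21 cognitive score earlier than Session 1 is named.

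**The concern.** In a two-level repeated-measures model, a covariate that is itself one of the two outcome levels changes what the within-person main effect tests. Without it, the Abstinence effect is the average Session 1 to Session 8 change. With it, the effect is the predicted change at covariate value zero. If the covariate is not centred, that is a person with a baseline score of zero, for whom regression to the mean predicts a change even when the average change is nil. If it is centred, the estimate is right but its standard error is too small.

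Abstinence is one of the two factors named for this analysis, and impaired cognition during abstinence is a posited relapse mechanism. The same model would be applied to several cognitive tasks, so an artefact could recur across them and look like consistent evidence.

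**Working it through.** The plan states no power or effect size for the cognitive ANOVA, so there is no figure to reproduce. The check is algebra plus simulation.

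**Inputs from the plan.** Two groups; 48 randomized ("A total of 48 randomized participants are planned for the R21 phase"), taken as 24 per group; significance at .05, taken as two-sided.

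**Assumed, because the plan gives neither.** Session 1-8 correlation r of .3 to .9, and baseline mean/SD of 0.5 to 10. Response times and error counts are both among the cognitive measures, so a wide mean/SD range is reasonable.

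**1. What is tested.** Let D = Y8 - Y1. The Abstinence test is the intercept, and the Group x Abstinence test the Group coefficient, in D regressed on effect-coded Group. The planned covariate adds Y1 to that regression.

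**2. Uncentred covariate.** With no true change, the expected intercept is (1 - r) x mean, which is not zero when r < 1 and the mean is not zero. Its approximate standard error, in SD units, is sqrt[(1 - r²)(1 + (mean/SD)²)/n]. At r = .7, mean/SD 3.3 and n = 48:
- expected intercept: .3 x 3.3 = 0.99 SD;
- standard error: sqrt(.51 x 11.89/48) = 0.36 SD;
- ratio about 2.8, so rejection is likely although nothing changed.

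**3. Centred covariate.** The intercept is the mean change. Its true variance is 2(1 - r)σ²/n, but the model uses (1 - r²)σ²/n. The ratio of model to true variance is (1 + r)/2, so the actual level is 2[1 - Φ(1.96 sqrt((1 + r)/2))]. This gives .114 at r = .3, .090 at .5, .071 at .7, .063 at .8 and .056 at .9.

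**4. Simulated false-positive rate of the Abstinence main effect**, n = 48, no true change (accurate to a percentage point or two):

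| Covariate | r = .7 | r = .8 | r = .9 |
|---|---|---|---|
| Uncentred, mean/SD 0.5 | 25% | 17% | 10% |
| Uncentred, mean/SD 1 | 52% | 36% | 20% |
| Uncentred, mean/SD 3.3 | 75% | 57% | 32% |
| Uncentred, mean/SD 5 | 77% | 58% | 32% |
| Mean-centred | 7-8% | 6% | 5% |
| None | 5% | 5% | 5% |

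At r = .7 the uncentred rate barely moves between mean/SD 5 and 10.

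**5. Fewer completers.** At mean/SD 3.3 and r = .7, .8 and .85, the uncentred rates are 62%, 45% and 34% at an assumed n = 36, and 44%, 30% and 23% at n = 24.

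**6. Masking.** Suppose a true decline of 0.5 SD, r = .7 and mean/SD 5. The uncentred test examines .3 x 5 - 0.5 = +1.0 SD, the opposite sign from the true change. It rejects in 44% of runs, against 99% for the test without the covariate. At mean/SD 3.3 it rejects in 27%.

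**7. Group tests.** Because Y1 is in the model, regressing D or Y8 on Group and Y1 gives the same Group coefficient and residuals. The Group x Abstinence t is therefore the Session 8 ANCOVA t. Simulated level is .050-.052; for a 0.5 SD interaction at r = .7, power is .65 with the covariate and .59 without. For the average (Y1 + Y8)/2, the Group coefficient and residuals are both halved, so the Group main effect has the same t again. At Session 1 the outcome equals its covariate, so a Group comparison there is degenerate.

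**The case against.** The best defence is that the wording is shorthand. One sentence covers several outcomes, and the parenthesis may simply mean a baseline-adjusted Session 8 comparison, which is sound. The plan is also silent on centring, and silence is not a decision to leave the covariate uncentred. Both points stand as reasons for moderation. Neither removes the problem: the sentence as written keeps Session 1 as an outcome level, and the R21 plan mentions standardizing only for the mediation models.

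A reader might infer more than the documents support:

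- **That the Abstinence test is invalid outright, or that a significant effect appears by construction.** The size depends on centring, r, mean/SD and the number of completers. A centred analysis with high r is nearly correct, and an uncentred one can hide a real change as well as create a false one.
- **That the medication comparison is compromised.** It is not; the interaction test keeps its level. Cognition is also an exploratory target, outside both the go/no-go rule and the targets in the power statement.
- **That the plan commits to comparing groups at Session 1.** It says only simple effects tests. The degeneracy matters only if that contrast is run; the Group contrast at Session 8 is unaffected.
- **That n = 48 is the analysis size.** Only continuously abstinent participants repeat the Session 1 procedure at Session 8, so 48 is a ceiling and the expected number is not stated.

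It is also fair to say that a correctly calibrated Abstinence test would not isolate abstinence, since Session 1 precedes medication and Session 8 follows repeat testing on VAR or PLA.

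**Conclusion.** The point holds for the Abstinence main effect on cognitive scores and for the within-group Session 1 versus 8 contrasts. It is a minor specification error, confined to an exploratory target.

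The inflation is slight with a centred covariate and severe without one; which applies cannot be told from the plan. The ranges rest on the assumed correlation, score scale and completer number, so they show how far the test could be off rather than predict this trial's error rate. The Group main effect and the Group x Abstinence interaction are one test and should not be reported as two findings. That the interaction is valid, and identical to the Session 8 ANCOVA, is exact and needs none of these assumptions.

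**What to change.** Take cognitive scores out of the 2 x 2 sentence and state that Session 8 scores will be analysed by ANCOVA on Group, with the Session 1 score as covariate. If an abstinence effect is wanted, test the Session 1 to Session 8 within-person change in a model without the Session 1 covariate, and note that this change also includes medication and practice effects.

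If another arrangement was intended, such as Session 2 versus Session 8 with Session 1 as covariate, name the sessions and the covariate and say that it is centred.

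The cost is a sentence or two in the analysis plan. The VAR versus PLA test, its power and the sample size do not change, and no extra data are needed.

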Analyses will examine (1) the effects of the study conditions on smoking measures (CO levels, cigarettes per day) and the target mechanisms (craving and negative affect during abstinence, reinforcing effects of a smoking lapse, cognitive function); (2) the extent to which the effects of the treatment conditions on smoking are mediated through the effects on the target mechanisms; and (3) the feasibility and acceptability of a multi-week VAR + mCM intervention in SS.

Primary and Secondary Outcome Measures

Primary Outcome Variables:

- Primary target measures: Questionnaire on Smoking Urges (QSU) total score, Minnesota Nicotine Withdrawal Scale (MNWS) negative affect score (average of the anger, depression, anxiety and difficulty concentrating items).
- Secondary target measures: Cigarette Evaluation Questionnaire (CEQ) Satisfaction scale (mean of ratings on the satisfaction, taste and enjoyment items), Reward scale (mean of ratings on the calm, feel more awake, less irritable, help to concentrate and reduce hunger items), and Craving Reduction scale (single item).
- Latency to relapse (hours between the start of Session 8 and time of relapse, collected in person at Friday's session and by videoed CO sample in the follow-up week).

Secondary Outcome Variables:

- Expired breath carbon monoxide (CO) level
- Salivary cotinine level
- Cognitive performance measures (response times, errors of omission, errors of commission) on the WAIS-IV Coding task, Continuous Performance Test-3, 2-letter search task, WAIS-IV letter-number sequencing task, Wisconsin Card Sorting Task
- Diener and Emmons Mood Scales
- Cigarette Evaluation Questionnaire (CEQ) Enjoyment of Respiratory Sensations scale (single item) and Aversiveness scale (mean of ratings on the dizziness and nausea items).
- MNWS items not included in primary variables: insomnia, restlessness, increased appetite
- Demand indices on the Cigarette Purchase Task (CPT): intensity (consumption at zero price), Omax (maximum amount of money allocated to cigarettes), break-point (first price at which participant reports zero consumption) and Pmax (price at which Omax occurs).
- Other smoking measures: Fagerström Test for Nicotine Dependence (FTND), Smoking Stage of Change questionnaire, Contemplation Ladder
- Psychiatric symptom measures: Brief Psychiatric Rating Scale (BPRS), Calgary Depression Scale for Schizophrenia

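### Latency to relapse, an R21 primary outcome, is named inconsistently and declared censored at 192 h, but its planned analyses carry no censoring and no rule covers early video loss

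*Combined protocol and SAP*

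**What the plan says.** The list of Primary Outcome Variables includes "Latency to relapse (hours between the start of Session 8 and time of relapse", and Aim 2 of the R21 phase asks whether the effect of VAR on time to relapse is mediated through the target mechanisms.

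The event is then named in several ways:

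- The R21 procedures in the Summary of the Protocol distinguish two events: "time of first lapse (single cigarette) and relapse (return to regular smoking) will be collected among those who have lapsed and relapsed".
- The Data Analysis Plan (R21 phase) first defines latency to relapse. Its next step is that "the maximum latency until second lapse will be 192 h, at which point data will be censored". The test follows: "Lapse latencies will be compared in VAR vs. PLA using a t-test".
- The sample-size section expects to "detect medium-sized group effects on latency to second lapse".
- The mediation paragraph speaks of both lapse latency and relapse latency.

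Three analyses of latency are planned: the t-test, a mediation macro resting on c − c' = ab, and a step-wise regression on BPRS scores.

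On who is followed, the procedures say that "participants who have been continuously abstinent will complete the same procedure as in Sessions 1". The sample-size section plans to enrol "up to 60 participants (30 per group) to include 48 in the intent-to-treat sample". Follow-up videos are twice daily for a week, each paid at $5 whatever the CO reading. No R21 text says how to score a participant whose videos stop early. The DSMB section (Monitoring activities) leaves missing data to the Board without stating a rule, and baseline imputation is specified for the R33 phase only.

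**The concern.** Two analysts following this text could build different outcome variables. One cigarette after Session 8 is a lapse; on the protocol's own distinction it is not a relapse. Second lapse may mean the next smoking after the scheduled Session 8 cigarette. That is still not a return to regular smoking, and the term does not fit participants who opt out of smoking at Session 8.

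The plan also says that data are censored and then uses methods that cannot represent censoring. A participant last known not to have relapsed at, say, 60 h must be entered at 60 h, entered at 192 h, or dropped. Nothing fixes the choice in advance, so it could be made after the data are seen. Because the clock starts at Session 8, it is also unclear whether randomised participants who were not abstinent then, or were absent, have a latency at all.

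**Working it through.** **The plan's own figure.** Session 8 (Thursday) to Friday is 1 day, plus 7 days of videos: 8 × 24 = 192 h. This reproduces.

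**Inputs.** From the documents: 48 randomised, taken as 48/2 = 24 per arm; 192 h horizon; significance at 0.05 (two-sided assumed). Assumed, because the documents give no figures: exponential relapse times, placebo median 96 h unless stated, hazard ratio 0.5 or 1, loss times uniform from 24 to 192 h, and the loss-prone fractions shown.

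**One participant's leverage.** Someone not relapsed on Friday (about 24 h) who sends no video moves the arm mean by (192 − 24)/24 = 7.0 h, depending on which value is entered. Four such participants in one arm move it by 4 × 7.0 = 28 h.

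**True effect under the assumptions.** Mean latency restricted to 192 h is (1 − e^(−192λ))/λ.

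- Placebo, λ = ln 2/96: 0.75 × 96/0.693 = 103.9 h.
- VAR, λ = ln 2/192: 0.50 × 192/0.693 = 138.5 h.
- Difference: about 34.6 h.

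**Complete follow-up, non-relapsers entered at 192 h.** Over placebo medians of 24, 48, 96 and 150 h, the t-test's type I error is 0.048–0.052. Its power is 0.62, 0.55, 0.41 and 0.32, against 0.64, 0.60, 0.47 and 0.37 for log-rank. Log-rank is slightly liberal at this size (0.053–0.060). With size matched, its gain is −1.5 to +5 points.

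**Early loss, by scoring rule (simulated).**

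| Scenario (VAR/PLA loss-prone) | Time of loss entered | 192 h entered | Dropped | Log-rank |
|---|---|---|---|---|
| HR 0.5, 20%/10%: difference | 27 h | 35 h | 31–32 h | – |
| HR 0.5, 20%/10%: power | about 0.28 | 0.41 | about 0.31 | 0.44 |
| No effect, 20%/10%: difference | −3.7 h | +1.2 h | −3.5 h | – |
| No effect, 35%/15%: difference | −6.7 h | +3.0 h | −7.2 h | – |

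In the 20%/10%, HR 0.5 row, only about 14% and 5% are actually lost before relapse. Type I error is 0.045–0.054 under every rule when loss is equal, 0.051–0.054 at 20%/10%, and 0.051–0.067 at 35%/15% (up to 0.077 at a placebo median of 150 h). Reversing the imbalance to 15%/35% reverses the signs.

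**Mediation.** With 30% loss in each arm and time of loss entered, the mediator slope shrinks to 0.83–0.87 of its full-data value. Pseudo-values of restricted mean latency recover 0.996–1.003 of it, and they equal the planned outcome if nobody is lost.

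**Session 8 population.** Assume 40% of PLA and 20% of VAR are not abstinent, placebo relapse is 70% by 192 h, and there is no later effect. Scoring the non-abstinent as 0 h gives a 22 h difference and 17% rejection; excluding them gives 0 h and 4%. Exclusion is not always neutral. If relapse-proneness varies between people (frailty variance 0.5–2) and abstinence is 50% on PLA, the bias is zero at 50% abstinence on VAR, −2 to −6 h at 55%, and −6 to −17 h at 65%.

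**Power statement.** For a two-sided t-test at 80% power, the detectable d is 0.83 with 24 per arm, 1.02 with 16 and 1.20 with 12. Reading medium as d = 0.5, power with 24 per arm is 0.40.

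**The case against.** *The event is defined.* The analysis section defines relapse explicitly, the aims agree, and the mediation paragraph uses lapse and relapse latency for one model. A reader might infer that three outcomes are planned. The documents do not support that: this is most likely loose wording for one variable. It still needs correcting, because the procedures record the two events separately.

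*The t-test is not wrong.* A reader might infer that censoring at 192 h invalidates it. With everyone followed to 192 h, and non-relapsers entered at that value, it is a valid comparison of restricted means. Under the assumed 20%/10% loss, entering 192 h gives 35 h and power 0.41 against 0.44. So a stated scoring rule alone would repair most of the group comparison. This objection stands for the t-test. It does not supply the missing rule, and the mediation model remains sensitive to how loss is scored.

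*Loss may be rare.* Payment regardless of CO makes early stopping less likely: 2 × 7 × $5 = $70 for a full set. That reduces the risk without excluding it.

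*The Session 8 start is by design.* A reader might infer a breach of intent-to-treat. The explicit commitment to include all randomised participants appears only under the R33 phase, and in R21 the term appears in sample-size wording. A latency that starts at Session 8 can reasonably be conditional on abstinence there. This is mainly a labelling matter.

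**Conclusion.** The point holds and should be fixed before the R21 blind is broken. A primary outcome, which is also the dependent variable of Aim 2, is worded inconsistently. It is declared censored, but its three analyses carry no censoring and no rule covers early loss.

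The size is conditional. With complete follow-up, the choice of test costs only a few points of power. With unequal early loss, the estimate moves by several hours and its sign under no effect depends on the rule. All relapse, loss and abstinence rates used here are assumed, so the actual size and direction of any bias are unknown.

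Two stronger inferences should not be drawn. The R33 decision is not compromised, because the go/no-go rule uses the primary and secondary targets and not latency. And d = 0.83 is not the trial's detectable effect: it applies only to a t-test on all 24 per arm. The plan's statement about medium-sized effects gives neither d nor power; 0.5 and 80% are readings supplied here.

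**What to change.** 1. **Event.** Use relapse, the defined event, in the sample-size, analysis and mediation text. State what observation counts as a return to regular smoking and how it is dated from Friday's report and the videos. Do not count the scheduled Session 8 cigarette.
2. **Group comparison.** Use Kaplan-Meier with log-rank or Cox. Censor early stoppers at the last contact at which they were known not to have relapsed, and other non-relapsers at 192 h. Add a sensitivity analysis counting early stoppers as relapsed at that contact. Report the restricted mean difference to 192 h descriptively. A permutation p-value is optional, given the slight liberality of log-rank.
3. **Mediation and BPRS regression.** Use a censoring-aware latency outcome. Pseudo-values of restricted mean latency, computed within arm, are one option and keep the linear c − c' = ab structure.
4. **Population.** Report the proportion of each randomised arm abstinent at Session 8. Label the comparison as conditional on that abstinence if only abstinent participants enter it. An all-randomised analysis is optional and for sensitivity only, since it mixes attaining abstinence with keeping it.
5. **Power statement.** Delete it, or restate it for the test and number actually analysed.

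**Cost.** No new visit or measure; revised wording, and somewhat more analysis than the planned SPSS procedures. Coverage of the bootstrap interval for ab with pseudo-values has not been checked.

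**Limit.** Censoring assumes that loss is unrelated to relapse. If 20% of VAR and 10% of PLA relapsers stop unseen, it gives a false gain of about 6 h under no effect. At 40%/20% the false gain is 14–16 h, with rejection of 0.11–0.12. The counted-as-relapsed sensitivity analysis brings this to within about 1 h (rejection 0.05–0.06), so it should be reported alongside.
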